7.4 Schema – Aim 2:Vaccine Evaluation
Aim 2: Vaccine Evaluation

Requirement	Pre-entry	Day 1	Dose #2	Dose #3	Month 7	Month 24	PSD*
Verification of eligibility (Protocol Sections 3.2 and 3.3)	X						
Permission for participation from treating clinician	X						
Informed consent/assent		X					
Medical record abstraction: Cancer Treatment Summary Form (Appendix 7)					X		
Patient/parent education (Appendix 12, 13)		X	X	X			
Targeted review of systems Screening for acute illness Screening for pregnancy (if indicated) Vaccine Visit Form (Appendix 8)		X	X	X			
HPV Vaccine		Dose #1	Dose #2	Dose #3			
Vaccine Report Card (Appendix 14) x 7 days (if enrolled after 3-1-16) or 14 days (if enrolled on or before 3-1-16) post each vaccine dose, including home temperature monitoring 4 hours after each vaccine dose, then daily x 5 days		X	X	X			
Quantitative Ig [humoral immunity]		X					
Anti-HPV 4cLIA (if enrolled on or before 3-1-16) or 9cLIA (if enrolled after 3-1-16) [geometric mean titers and HPV type-specific seropositivity]		X			X	X	X
HPV-specific total immunoglobulin [qualitative aspects of HPV-specific humoral response]						X	
Adverse Events/Research-Related Problems Form (AERF; Appendix 15)		→	→	→	→	→	→
Month 7 Visit Form (Follow-Up #1) (Appendix 9)					X		
Month 24 Visit Form (Follow-Up #2) (Appendix 16)						X	
Premature Study Discontinuation (PSD) Form (Appendix 10) [†]							X

*PSD = Premature Study Discontinuation (collected at PSD clinic visit or when deemed lost to follow-up; see Section 5.4.12)

→ = AERF to be completed as needed at any study time point

[†]PSD Form will also be completed as needed at any time point that participation is terminated prematurely

8.0 STATISTICAL METHODS

8.1 Sample Size

Aim 1 (Survey): A sample size of 1090 eligible subjects is required to address Specific Aim 1. We have chosen this sample size based on our preliminary study (Section 2.9), from which we can assume that 90% (n=981) of those approached will participate in the survey. A sample of 981 survey participants for Specific Aim 1 will provide 80% power to reject the null hypothesis that the prevalence (p) of HPV vaccine initiation is ≤ 0.4 if the true p is at least 0.44 (one-sided test, Type I error=0.05). It will also provide a 2-sided 95% confidence interval (CI) of sample $p \pm .061$ if true $p=0.4$.

[Protocol v3, 8/17/15: Accrual goal for Aim 1 met, enrollment to survey closed]

Aim 2 (Vaccine Evaluation):

qHPV Vaccine Cohort (patients enrolled on or before 3-1-16): Based on national vaccine initiation rates and our preliminary data (Section 2.9),⁴⁰ we conservatively assume that 60% (n=589) of the 981 survey participants will have not initiated the HPV vaccine. Based on our data (Section 2.9) and prior trials,^{30,31,135} we conservatively assume that of the non-vaccinated survey participants, 60% (n=353) will agree to receive the vaccine, 96% (n=339) will be seronegative at baseline (Intent to Treat [IT] sample), and 92% (n=312) will complete all 3 doses, yielding 312 (Per-Protocol [PP]) subjects who will have received all 3 doses of qHPV vaccine for examining Aim 2.1. This sample size was calculated using the mean GMT and SD reported by Merck & Co.²⁸ for healthy males and females aged 9-15 years and 16-26 years as the historical healthy population. The following assumptions were made: i) cancer survivors were similarly distributed in regard to immunogenicity with the same SD as in this healthy population; ii) margin of equivalence (E) was $\frac{1}{2}$ of the mean GMT of the healthy population (Table 7). Using the method of Korn and Freidlin¹³⁶ for sample size calculations using historical controls, a total of 312 subjects (72 younger females, 77 older females, 82 younger males, and 81 younger males) will provide 80% power to demonstrate non-inferiority with respect to anti-HPV-16, and/or -18 GMT in cancer survivors compared to the healthy population assuming a one-sided t-test, Type I error =0.00312 (for an overall Type I error =0.025), and margin of equivalence (E) shown in Table 7 by sex and age for each vaccine type.

Table 7. Sample Size for Aim 2 (Vaccine Evaluation)

		Females								
Anti-HPV	9-15y (younger)					16-26y (older)				
	Healthy	Cancer	E	SD	N	Healthy	Cancer	E	SD	N
16	4918.5	2459.3	2459.25	5585.26	72	2411.3	1205.65	1205.65	2915.77	77
18	1042.6	521.3	521.30	1161.91	69	475.6	237.80	237.80	500.01	58
		Males								
16	6056.5	3028.3	3028.25	6895.81	72	2401.5	1200.75	1200.75	2747.45	72
18	1357.4	678.7	678.70	1641.08	82	402.6	201.30	201.30	489.9	81

Sample size required = 312

The coordinating center will track enrollment to each stratum (Younger Females, Older Females, Younger Males, Older Males), and will close enrollment to each stratum once the targeted number of evaluable participants has been reached.

9vHPV Vaccine Cohort (patients enrolled after 3-1-16): Results of interim data analysis on the qHPV vaccine cohort (performed in January 2016 with data from patients who had a Month 7 sample available for analysis on or before 8-28-15; N=133) indicate that the cohort enrolled on or before 3-1-16 (N=254) who have received/are receiving the qHPV vaccine will be more than sufficient to address non-inferiority (i.e., lower limit of the multiplicity-adjusted 95% confidence intervals for the ratio of the mean geometric mean titer for anti-HPV-16 and -18 in the cancer vs. healthy population >0.5 for each

age/gender group) of the qHPV vaccine in cancer survivors. We are therefore extending the study to evaluate non-inferiority of the 9vHPV vaccine; interim data analysis results from the qHPV vaccine cohort indicate that an additional 200 patients will be sufficient to perform this evaluation in cancer survivors.

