Despite the excellent efficacy and safety profile of the qHPV vaccine in the general population, and 2006 recommendation by the Advisory Committee on Immunization Practices (ACIP) for routine vaccination of young females, only 44.3% of the 13- to 17-year old females have initiated the HPV vaccine series and only 26.7% have received all three doses.⁴⁰ There is paucity of data regarding HPV vaccine uptake in other age groups and none to date in males. Notably, there are no reports of the prevalence of HPV vaccine initiation or acceptability in cancer survivors. Despite their increased risk for HPV-related morbidity, it is possible that HPV vaccine uptake is even lower in cancer survivors than in the general population, due to reluctance on the part of patients/parents or clinicians when immunogenicity and safety/tolerability data for this population is lacking.

This trial uses an approach that combines a cross-sectional survey, to determine vaccine initiation rates in cancer survivors between 9 and 26 years of age who are between 12 and 60 months post completion of systemic therapy, to identify predictors of vaccine non-initiation in these survivors; and among cancer survivors identified to be unimmunized, a single arm phase II open-label trial, to determine the

immunogenicity and safety/tolerability of the qHPV vaccine (HPV-6, -11, -16, -18; Gardasil®; Merck Research Laboratories; for patients enrolled on or before 3-1-16) and the 9vHPV vaccine (HPV-6, -11, -16, -18, -31, -33, -45, -52 and -58; Gardasil®9; Merck Research Laboratories; for patients enrolled after 3-1-16), and simultaneously explore response persistence.

The primary aims of this study are to:

[figure not shown]
1. Using a cross-sectional survey approach, estimate the prevalence of HPV vaccine initiation in cancer survivors ages 9 to 26 years
 - a. Examine the sociodemographic, behavioral, and medical determinants of HPV vaccine non-initiation
2. Among cancer survivors identified to be non-immunized in Aim 1 and by additional methods, use a single-arm, phase II, open-label, prospective longitudinal trial design, to evaluate the 3-dose qHPV vaccine series (for patients enrolled on or before 3-1-16) and the 3-dose 9vHPV vaccine series (for patients enrolled after 3-1-16), and measure the following endpoints:
 - a. Determine immunogenicity following the third and final vaccine dose
 - b. Identify clinical/host factors influencing immunogenicity

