1.0 OBJECTIVES AND HYPOTHESES

Aim 1:

Using a cross-sectional survey approach, estimate the prevalence of HPV vaccine non-initiation

- a. Examine sociodemographic, behavioral, and medical determinants of HPV vaccine non-initiation

Hypothesis 1: The HPV vaccine initiation rates for cancer survivors will be less than 40% (estimated rate in the general population); subgroups of cancer survivors with particularly low vaccine initiation rates will be identified.

Among cancer survivors identified to be non-immunized in Aim 1, and among additional non-immunized cancer survivors meeting study eligibility criteria:

Aim 2:

Using a single-arm, phase II, open-label, prospective longitudinal trial design, to evaluate the 3-dose qHPV (for patients enrolled on or before 3-1-16) or 9vHPV (for patients enrolled after 3-1-16) vaccine series and measure the following endpoints:

- a. Determine immunogenicity following the third and final vaccine dose
- b. Identify clinical/host factors influencing immunogenicity
- c. Determine the safety/tolerability of the qHPV and 9vHPV vaccine in cancer survivors

Hypothesis 2: Immunogenicity to the qHPV and 9vHPV vaccines will be heterogeneous among cancer survivors, with subpopulations that received the most intense therapy demonstrating inferior immunogenicity. The qHPV and 9vHPV vaccines will be safe and well-tolerated by cancer survivors.

Exploratory sub-aim:

Evaluate the persistence of antibody response at 2 years post vaccine initiation and identify clinical/host factors influencing response persistence.

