2.9 Preliminary Studies

“HPV among Survivors of Childhood Cancer” (SJCRH-HPV-1; PI [name]; Co-Investigator [name]) is an IRB-approved and institutionally-funded exploratory study conducted at St. Jude Children’s Research Hospital. This pilot study aimed to estimate the prevalence of HPV vaccination and examine

predictors of vaccine initiation and intent in a cohort of cancer survivors from a single institution. As of 3-4-11, 220 parents (of female patients age 9-17) and 75 female cancer survivors (age 18-26) have been approached for participation in this study. Overall consent rate is 94.2% (95% for ages 9-17; 90% for ages 18-26) with an 86% survey completion rate. Reasons for non-participation (n=17) include “not interested” (88.2%) and “tired of filling out questionnaires” (11.8%). Self-/parent-reported HPV vaccine initiation rates in this cohort are 33.3% overall (33.1% for age 9-17; 38.9% for age 18-26), with lower vaccine initiation rates in patients with leukemia/lymphoma (29.0%) compared with solid tumors (38.2%). Vaccine initiation rates by race are 31.4% for Caucasians compared with 40.7% for all other races combined; initiation rates by religious preference are: Protestant 39.1%, Catholic 22.2%, Other 30%; and by annual income: <\$20K: 50%, \$20-99K:25.8%, ≥\$100K: 40%. When unimmunized survivors were asked how likely they were to initiate the vaccine in the future, 46.0% indicated “likely/very likely/definitely will”, 21.9% indicated “unlikely/very unlikely/definitely will not,” and 32.1% were “unsure”. When unimmunized survivors were asked about their willingness to receive the HPV vaccine in the setting of a clinical trial, 62.8% indicated willingness, 17.2% indicated unwillingness, 20.0% were unsure.

In the current study, we will expand upon this pilot initiative across geographically and racially/ethnically diverse populations in order to collect data that is generalizable to the broader cancer survivor population; and, for the first time, to include both males and females. Finally, we plan to explore predictors of vaccine refusal in unimmunized survivors (i.e., unimmunized participants will be offered the HPV vaccine after survey completion, and reasons for refusal will allow examination of translation of intent into action vs. refusal).

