8.2 Data Analysis

8.2.1. Aim 1 (Survey)

8.2.1.1. Estimate the prevalence of HPV vaccine initiation in cancer survivors ages 9 to 26 years. Examine the sociodemographic, behavioral, and medical determinants of HPV vaccine non-initiation

The outcome is HPV vaccine initiation status (Yes: received at least one dose/ No: never received any doses) at the time of survey completion. The prevalence (p) of qHPV vaccine initiation among 981 survey participants and its 2-sided 95% CI will be calculated. A one-sided t-test of $H_0: p \leq 0.4$ will be conducted using Type I error=0.05. Significant predictors of vaccine initiation will be identified using logistic regression. We will consider predictors relevant to vaccine acceptance or refusal, including sociodemographic (e.g., age, sex, education, race/ethnicity, income), medical (e.g., cancer diagnosis, intensity of treatment, conventional treatment vs. HCT), and behavioral (e.g., perceived susceptibility to HPV, perceived severity of consequences of HPV infection, attitudes toward vaccination, attitudes toward healthcare provider recommendation of vaccine, engagement in health promotion behaviors, knowledge regarding association of HPV with cancer, familial decision-making style). A sample size of 981 will provide 80% power at 5% significance level to detect an odds ratio of 1.45 to 2.0 for a dichotomous variable with 50% of the sample in one group.

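### The one planned test of Aim 1 uptake against 40% runs in the wrong direction: it can only show initiation above 40%, while Hypothesis 1 says it is below

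*Combined protocol and SAP*

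**What the plan says.** Section 1.0 gives Hypothesis 1 as a directional claim: "The HPV vaccine initiation rates for cancer survivors will be less than 40% (estimated rate in the general population").

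Section 8.1 sizes the survey at 981 participants (90% of 1090 approached). It states that this number gives 80% power, one-sided at 0.05, to "reject the null hypothesis that the prevalence (p) of HPV vaccine initiation is ≤ 0.4 if the true p is at least 0.44".

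Section 8.2.1.1 carries the same null into the analysis: "A one-sided t-test of $H_0: p \leq 0.4$ will be conducted using Type I error=0.05". It defines the outcome as initiation, meaning at least one dose received, so p is the initiation rate in both sections. It also says that the prevalence "among 981 survey participants and its 2-sided 95% CI will be calculated", and it plans logistic regression for predictors. Section 8.1 puts the half-width of that interval at .061 when the true rate is 0.4.

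Three further points bear on this:

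- The abstract lists Aim 1 first under "The primary aims of this study are to".
- Section 2.9 reports from the pilot that "HPV vaccine initiation rates in this cohort are 33.3% overall".
- Section 8.1 carries the note "Accrual goal for Aim 1 met, enrollment to survey closed", dated 8/17/15 (protocol v3).

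**The concern.** In a one-sided test, the claim to be demonstrated belongs in the alternative. Here the claim, initiation below 40%, lies wholly inside the null. Rejection would contradict Hypothesis 1, and non-rejection would leave it undecided.

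The stake is the formal conclusion of a primary aim. The stated 80% power is power to reach the opposite finding. A non-significant result could be read as confirming low uptake, although the test returns that result quite often when uptake is above the benchmark. The confidence interval is still informative, but the plan does not say what interval would count as support.

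**Working it through.** **Inputs.** n = 981, benchmark p0 = 0.40, one-sided alpha = 0.05 and planning value 0.44 (section 8.1); pilot rate 0.333 (section 2.9). The rates 0.36 and 0.42 are illustrative: 0.36 mirrors 0.44 on the other side of 0.40, and 0.42 is a true rate modestly above the benchmark.

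**1. Reproduce the plan's power.**

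- Standard error under the null: √(0.4 × 0.6 / 981) = 0.01564. At p = 0.44: √(0.44 × 0.56 / 981) = 0.01585.
- Upper-tail power = Φ[(0.04 − 1.645 × 0.01564) / 0.01585] = Φ(0.900) = 0.816.
- Exact binomial: reject at 419 or more of 981 (42.7%), actual alpha 0.0448, power at 0.44 = 0.801.
- A two-sided version gives 0.722, which does not match.

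The stated 80% is therefore right for a one-sided test of p > 0.4. The reversal is in the design calculation as well as in the wording.

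**2. What the written test can show (exact binomial).**

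| True initiation rate | Probability of rejecting p ≤ 0.4 |
|---|---|
| 0.333 (pilot) | 5 × 10⁻¹⁰ |
| 0.36 | 9 × 10⁻⁶ |
| 0.39 | 0.0096 |
| 0.40 | 0.045 |
| 0.42 | 0.337 |
| 0.44 | 0.801 |

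Every count from 0 to 418 gives the same non-rejection. At a true rate of 0.42 the probability of non-rejection is 1 − 0.337 = 0.663 exact, or 0.642 by the normal approximation.

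**3. The reversed test, H0: p ≥ 0.4 against p < 0.4, same n and alpha.**

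- Exact cut-off: 366 or fewer of 981 (37.3%), actual alpha 0.0453.
- Exact power: 0.813 at 0.36, 0.800 at 0.3607, 0.996 at 0.333.
- Normal approximation at 0.36: standard error √(0.36 × 0.64 / 981) = 0.01533, so Φ[(0.04 − 0.02573) / 0.01533] = Φ(0.931) = 0.824.

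**4. The planned two-sided 95% interval used as a decision rule.**

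- Its upper limit is below 0.40 at 362 or fewer of 981 (36.9%), by either the Wald or the Wilson interval. Wald at 362: 0.3690 + 0.0302 = 0.3992.
- Probability that the rule is met: 0.025 at 0.40, 0.733 at 0.36, about 0.80 at 0.3567, and 0.992 at 0.333.

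**5. The interval's stated precision.**

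- Half-width at p = 0.4: 1.96 × 0.01564 = 0.0307. Full width: 0.0613.
- The printed .061 matches the full width. As a half-width it would correspond to about 0.24 × (1.96 / 0.061)² ≈ 248 participants, not 981.
- If the half-width really were .061, an upper limit below 0.40 would need a sample rate below 0.40 − 0.061 = 33.9%.

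**The case against.** The strongest reply is that Aim 1 is worded as estimation. The first analysis listed is the prevalence with its two-sided interval, which does not depend on the direction of any null. A reader with that interval would not be misled: an observed 42% gives about 0.389 to 0.451, and at a true rate of 0.42 the chance that the upper limit falls below 0.40 is about 0.0006. The sample size is almost equally good in either direction (exact power 0.801 at 0.44 and 0.813 at 0.36). Aim 2 recruitment does not depend on this test, and the logistic regression is unaffected. All of that stands. It shows that the data and the estimate remain sound, and that the repair is small.

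It does not rescue the test. The plan attaches a directional hypothesis, an alpha and a power statement to Aim 1, and all the formal machinery points the wrong way. The interval could do the job, but the plan does not assign it that job.

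A second reply is that section 7.2 names the endpoint as non-initiation, and section 1.0 words Aim 1 the same way. For non-initiation an upper-tail test would be correct, with a null of at most 0.6 and power of about 0.82 at 0.64. A mix-up between the two codings may explain the error, though that is inference. The printed figures are 0.4 and 0.44, and both statistical sections define p as initiation, so the contradiction remains.

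The interval's half-width is a separate slip. It adds nothing to the case about direction, but it sits in the same paragraph and should be corrected with it.

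**Conclusion.** The concern holds. The only planned test of overall prevalence against 40% cannot support Hypothesis 1 at any survey result, and the 80% power in section 8.1 belongs to the opposite conclusion. Because this is the formal test of a primary-aim hypothesis, it must be corrected before Aim 1 is reported.

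The damage is limited to inference about the benchmark. The sample size, the prevalence estimate, its interval once computed from the data, and the predictor analysis are unaffected. The power figures assume simple binomial sampling of 981 evaluable participants and 0.40 treated as a fixed benchmark, as the plan does.

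**What to change.** Make one of two changes in both 8.1 and 8.2.1.1.

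1. **Reverse the test.** State H0: p ≥ 0.4 against H1: p < 0.4, one-sided alpha 0.05, by an exact binomial or score test. Restate the power as about 80% at a true initiation rate of about 0.36 and over 99% at the pilot's 33.3%. At this sample size the move away from a t-test is a matter of tidiness; the direction is what matters.
2. **Use the interval.** Prespecify that Hypothesis 1 is supported if the upper limit of the planned two-sided 95% interval is below 0.40. This amounts to one-sided alpha 0.025 and gives 80% at a true rate of about 0.357. It uses an analysis already in the plan and avoids choosing a one-sided direction late, which makes it the easier option to defend now.

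In either case, correct the half-width in 8.1 from .061 to .031, and say in both sections that p is initiation while the endpoint in 7.2 is its complement.

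The cost is wording and a dated amendment entry, with no new data and the same n. The survey had closed by protocol v3, and the documents do not say whether its results had been seen. The entry should therefore present the change as a correction to match the Hypothesis 1 already stated, and should disclose whether Aim 1 results were known when it was made.

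### Aim 1 precision is stated as ±0.061, but at n = 981 and p = 0.4 the 95% half-width is ±0.031; the printed figure matches the full width of the interval

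*Combined protocol and SAP*

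**What the plan says.** The Aim 1 paragraph of Section 8.1 (Sample Size) starts from 1090 eligible subjects and assumes 90% participation, which gives 981. It makes two claims for those 981.

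- **Power.** "A sample of 981 survey participants for Specific Aim 1 will provide 80% power". The null is an initiation prevalence of 0.4 or lower, the alternative is 0.44 or higher, and the test is one-sided at α = 0.05.
- **Precision.** "It will also provide a 2-sided 95% confidence interval (CI) of sample". The interval is then written as the observed prevalence plus or minus 0.061, for a true prevalence of 0.4.

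Section 8.2.1.1 plans the same interval on the whole sample: the prevalence "among 981 survey participants and its 2-sided 95% CI will be calculated". That section gives no precision figure, so the number to correct appears only in Section 8.1. Neither section mentions a design effect, an adjustment for clustering by site, or a subgroup to which the interval would apply.

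**The concern.** A figure after a ± sign is read as a half-width. With close to 1,000 respondents and a prevalence near 0.4, a 95% half-width should be about three percentage points, not six.

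Prevalence of vaccine initiation is the first primary aim, and this is the only precision given for it. Someone comparing the eventual published interval with the plan would find it half as wide as promised. They would then have to ask whether the sample, the method or the confidence level had changed. Someone using the plan to size a similar survey would be misled by a factor of two in precision, and so about four in sample size.

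The figure also sits awkwardly beside the power claim. With ±0.061, an observed prevalence of 0.44 would have an interval of 0.379 to 0.501, which includes the null value of 0.40. The preceding sentence offers 80% power to reject 0.40 at that same true prevalence.

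**Working it through.** **Inputs, all from Section 8.1:** n = 1090 × 0.90 = 981; true p = 0.4 for the interval; two-sided 95% confidence, so z = 1.96; power claim p0 = 0.40, p1 = 0.44, one-sided α = 0.05, so z = 1.645.

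**1. The stated precision.**

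- Standard error = sqrt(0.4 × 0.6 / 981) = 0.01564
- Half-width = 1.96 × 0.01564 = **0.0307**
- Full width = 2 × 0.0307 = **0.0613**

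The printed 0.061 is not reproduced as a half-width. It agrees with the full width to three decimals.

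**2. Whether another standard calculation gives ±0.061.**

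| Variant | Half-width |
|---|---|
| Wald, n = 981, p = 0.4 | 0.0307 |
| Wilson | 0.0306 |
| Continuity-corrected | 0.0312 |
| Clopper-Pearson (392/981) | 0.0311 |
| Wald, p = 0.44 | 0.0311 |
| Wald, p = 0.5 (widest case) | 0.0313 |
| Wald, n = 1090, p = 0.4 | 0.0291 |
| Wald, n = 589 (assumed unvaccinated), p = 0.4 | 0.0396 |
| Wald, n = 353 (assumed to accept vaccine), p = 0.4 | 0.0511 |
| Wald, n = 312 (Aim 2 per-protocol), p = 0.4 | 0.0544 |

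None reaches 0.061. Every 95% variant at n = 981 lies between 0.0306 and 0.0313. To obtain ±0.061 at p = 0.4 one would need one of the following:

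- a sample of 0.24 × (1.96 / 0.061)² = **247.8**, about 248 respondents;
- at n = 981, a design effect of (0.061 / 0.03066)² = **3.96**; or
- at n = 981, a confidence level of about 99.99%.

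**3. The power claim beside it, at n = 981.**

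Power = Φ{[(p1 − p0) − 1.645 × sqrt(p0(1 − p0)/n)] / sqrt(p1(1 − p1)/n)}

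- 1.645 × sqrt(0.24 / 981) = 0.0257
- sqrt(0.2464 / 981) = 0.01585
- Power = Φ[(0.04 − 0.0257) / 0.01585] = Φ(0.90) = **0.816**

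The exact binomial test (reject at 419 or more; attained α = 0.0448) has power **0.801**. The 80% claim therefore reproduces.

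**4. The same power at the sample size that ±0.061 implies (n ≈ 248).**

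- 1.645 × sqrt(0.24 / 248) = 0.0512
- sqrt(0.2464 / 248) = 0.0315
- Power = Φ[(0.04 − 0.0512) / 0.0315] = Φ(−0.35) = **about 0.36**

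A hidden design effect of 3.96 would cut the effective sample size to 981 / 3.96 ≈ 248 and lead to the same 36%. It therefore cannot reconcile the two sentences.

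**5. The interval as it should look.** At an observed 0.44 the interval is 0.44 ± 0.031, or 0.409 to 0.471. This excludes 0.40, in keeping with the power claim.

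**The case against.** The arithmetic is not in dispute; the best counter-argument is that nothing depends on the figure. The sample size is justified by the power claim, which reproduces, and the interval is mentioned only as a by-product. Section 8.2.1.1 computes the interval from the data, so the reported width will be right whatever Section 8.1 says. The error understates what the survey delivers, and Section 8.1 itself records that the Aim 1 accrual goal was met and enrollment closed. On this view the 248 respondents and 36% power are hypothetical, because the plan gives n = 981 throughout.

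That stands as a limit on the consequences. No one faces 36% power, and no recruitment decision changes. The 248 and 36% figures serve only to show that the two sentences cannot both describe the same sample, and the working shows that the precision sentence is the wrong one.

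Two further points are fair. The document does not say how 0.061 was obtained, so the full-width explanation is an inference from a close numerical match. And the power sentence has a separate problem of direction: Hypothesis 1 in Section 1.0 expects initiation below 40%, while the test looks for a prevalence above 0.4. That does not affect the half-width and is not settled by correcting it.

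**Conclusion.** The concern holds. The half-width of the two-sided 95% interval at n = 981 and p = 0.4 is ±0.031, so the printed ±0.061 is too large by a factor of two, and it is inconsistent with the power claim for the same participants. The conclusion assumes simple binomial sampling, as the plan's own calculation does, and does not depend on the choice among standard interval methods or on how the error arose. The practical effect is small: the stated precision is pessimistic, and neither the sample size nor the planned analysis changes.

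**What to change.** In Section 8.1, Aim 1, replace ± .061 with ± 0.031. Alternatively, keep the figure but describe it as the total width of the interval (0.061). If an allowance for clustering was intended, state the design effect and recompute the power on the same basis, since the current power figure contains no such allowance. Section 8.2.1.1 needs no change on this point.

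The cost is one number in the protocol, and the corrected figure is the more favourable one. No sample size, procedure or analysis is affected.

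### Section 8.1 attaches 80% power to the total of 312 subjects, but Table 7 gives about 80% only for each single type-by-stratum comparison; the plan should say so and state which success rule it means

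*Combined protocol and SAP*

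**What the plan says.** Section 8.1 (Aim 2, qHPV cohort) assumes that "cancer survivors were similarly distributed in regard to immunogenicity with the same SD as in this healthy population" and sets the margin E at half "of the mean GMT of the healthy population (Table 7"). It then gives, "for sample size calculations using historical controls, a total of 312 subjects" with "80% power to demonstrate non-inferiority with respect to anti-HPV-16, and/or -18 GMT in cancer survivors compared to the healthy population", using a "one-sided t-test, Type I error =0.00312 (for an overall Type I error =0.025"). The strata are listed as "72 younger females, 77 older females, 82 younger males, and 81 younger males"; Table 7 shows that the last group is older males. Table 7 prints a separate N for each of two HPV types in each of four strata.

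Further on in 8.1, under the 9vHPV cohort, the plan explains why 254 qHPV enrolments are judged enough. There it describes non-inferiority as a lower confidence limit "for anti-HPV-16 and -18 in the cancer vs. healthy population >0.5 for each" age/gender group.

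Section 8.2.2.1 analyses each vaccine component separately, with multiplicity-adjusted intervals for the GMT ratio and a lower limit above 0.5 as the criterion. It does not say how the eight results combine.

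**The concern.** The 80% is the only power figure given for the primary immunogenicity aim, and the sentence ties it to the whole sample and to cancer survivors in general. A reader could take it as the chance of meeting the both-types, each-group criterion that the same section describes. Table 7 was not sized for that. The and/or makes matters worse, because -16 or -18, -16 and -18, and each type on its own have different powers. The sufficiency statements for 254 qHPV patients and 200 further 9vHPV patients come with no power on any of these readings.

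**Working it through.** **Inputs.** E, SD and N are from Table 7. Alpha is 0.00312 one-sided (0.025/8 = 0.003125, so eight tests). The true difference is zero. Stratum sizes are 72, 77, 82 and 81. The documents do not give the size of the historical sample or the correlation between the two types. The first is back-solved below and the second is varied from 0 to 1. Strata contain different people and are treated as independent.

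**Step 1: reproduce Table 7.** With a finite historical sample Nh, power = Φ[(E/SD)/√(1/N + 1/Nh) − 2.735]. Solving for the Nh that gives 80% at each printed N gives about 790 to 2,600. Alternatively, treating the historical mean as fixed (one-sample noncentral t) needs no Nh and returns Ns within 3 of every printed value. Taking the larger N per stratum gives 308, against the plan's 312. So each Table 7 N is the size for about 80% power on one test.

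**Step 2: power per comparison at the planned stratum sizes (finite-Nh model).**

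| Stratum (n) | Type | E/SD | Table 7 N | Fixed-mean N | Power at n |
|---|---|---|---|---|---|
| Younger females (72) | 16 | 0.440 | 72 | 70 | 0.80 |
| | 18 | 0.449 | 69 | 68 | 0.82 |
| Older females (77) | 16 | 0.413 | 77 | 79 | 0.80 |
| | 18 | 0.476 | 58 | 61 | 0.91 |
| Younger males (82) | 16 | 0.439 | 72 | 71 | 0.86 |
| | 18 | 0.414 | 82 | 79 | 0.80 |
| Older males (81) | 16 | 0.437 | 72 | 71 | 0.85 |
| | 18 | 0.411 | 81 | 80 | 0.80 |

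**Step 3: all eight succeed, at 0.00312 per test.**
- Types independent: the product of the eight unrounded powers is 0.224.
- Types fully correlated within a stratum: the product of the four stratum minima is 0.80⁴ = 0.41.
- Intermediate correlation: 28% at 0.5 and 31% at 0.7.
- Fixed historical mean: 24.6% to 42.9%; simulation gives 25.0% to 42.9%.

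For comparison, the chance that at least one type succeeds in every stratum is about 55-89%.

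**Step 4: all eight succeed, at 0.025 per test.** On the fixed-mean model this is 74.8% to 83.1%. On the finite-Nh model, replacing 2.735 by 1.960 adds 0.775 to each z. A cell at 0.80 becomes Φ(0.842 + 0.775) = 0.947, and the fully correlated bound is 0.947⁴ = 0.80. The other four cells become 0.954, 0.984, 0.967 and 0.965, and the independent product is 0.80 × 0.954 × 0.984 × 0.967 × 0.965 = 0.70.

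**Step 5: sensitivity to scale (assumed, since the documents give no log-scale SD).** The criterion is a ratio above 0.5, so on natural logs the margin is ln 2 = 0.693. With a fixed historical mean, 312 subjects and 0.00312 per test:
- log SD taken as SD/mean (1.05 to 1.22): all-eight power 94-95%;
- titres lognormal with Table 7's mean and SD (log SD 0.86 to 0.95): above 99.9%.

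**Step 6: amended qHPV cohort.** Applying 8.1's planning rates, 254 × 0.96 × 0.92 ≈ 224 per-protocol subjects, split in the same proportions. At 0.00312 the finite-Nh raw-scale model gives 0.62 to 0.78 per comparison and 4-16% jointly. The two log-scale assumptions give 63-74% and 97-98% jointly. If all 254 were evaluable, the raw-scale joint figure would be 8-23%.

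**The case against.** The strongest reply is that the plan makes eight separate claims. The and/or, the eight-way split of alpha, the separate Ns in Table 7 and the component-by-component analysis in 8.2.2.1 all fit that reading, and 80% per comparison is then a legitimate design statement. The both-types, each-group wording appears in a parenthesis explaining the interim judgement on cohort size, and it can be read as a criterion applied group by group. This stands: no section makes success on all eight a single decision rule. It does not rescue the sentence in 8.1, which never says that the 80% is per comparison and attaches it to the total.

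A reader might go further and infer that the trial has only a 22-41% chance of answering its main question, or 4-16% with the amended qHPV cohort, so that failure is the likelier outcome. The documents do not support that, for three reasons. It combines an alpha meant for separate claims with an all-must-pass rule that would need no split. It uses raw-scale SDs larger than their means, whereas the planned analysis is of a GMT ratio, for which plausible log-scale SDs give far higher power. And the 4-16% rests on planning-stage evaluable rates and back-solved historical sample sizes, while the January 2016 interim results (N=133) that the plan cites for sufficiency are not shown and cannot be checked here.

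**Conclusion.** The concern holds as a mislabelled power statement. Table 7's arithmetic is sound, but it supports 80% (0.80 to 0.91) for each type-by-stratum comparison at one-sided 0.00312. It does not support 80% for both types in all four groups: on Table 7's own model that probability is about 22-43%, across the two treatments of the historical mean and any non-negative correlation between types. These joint figures assume raw-scale normality, true equality and independent strata. They show that the 80% cannot carry over to the joint criterion; they are not a forecast for the GMT-ratio analysis. Which figure matters depends on a success rule that the plan leaves open.

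**What to change.** In 8.1, restate the claim as 80% power for each type-by-stratum comparison at one-sided 0.00312, and drop the and/or. State in 8.1 and 8.2.2.1 whether non-inferiority is claimed comparison by comparison or only if all eight succeed.

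If the claim is joint, report its power under the chosen rule: 22-43% at 0.00312 per test, or about 75-83% at 0.025 per test (fixed historical mean; 70-80% with a finite historical sample). Label these as raw-scale Table 7 figures.

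Under either rule, add power on the scale of the planned GMT-ratio analysis, with the log-scale SD and the historical sample size stated. Give the same figures for the amended cohorts (254 qHPV, 200 9vHPV), with the assumed evaluable rates.

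The cost is a short recalculation and revised wording. Enrolment does not change; the analysis would change only if the sponsor chose the joint rule and dropped the alpha split.
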